#### **17.4.1.12. Obesity**

##### **17.4.1.12.1. ICD-10-CM Codes**

- E66.0 Obesity due to excess calories
- E66.01 Morbid (severe) obesity due to excess calories
- E66.09 Other obesity due to excess calories
- E66.1 Drug-induced obesity
- E66.2 Morbid (severe) obesity with alveolar hypoventilation
- E66.8 Other obesity
- E66.9 Obesity, unspecified

#### **17.4.1.13. Type 2 Diabetes**

##### **17.4.1.13.1. ICD-10-CM Codes**

- E11.00 Type 2 diabetes mellitus with hyperosmolarity without nonketotic hyperglycemic-hyperosmolar coma (NKHHC)
- E11.01 Type 2 diabetes mellitus with hyperosmolarity with coma
- E11.10 Type 2 diabetes mellitus with ketoacidosis without coma

- E11.11 Type 2 diabetes mellitus with ketoacidosis with coma
- E11.21 Type 2 diabetes mellitus with diabetic nephropathy
- E11.22 Type 2 diabetes mellitus with diabetic chronic kidney disease
- E11.29 Type 2 diabetes mellitus with other diabetic kidney complication
- E11.311 Type 2 diabetes mellitus with unspecified diabetic retinopathy with macular edema
- E11.319 Type 2 diabetes mellitus with unspecified diabetic retinopathy without macular edema
- E11.321 Type 2 diabetes mellitus with mild nonproliferative diabetic retinopathy with macular edema
- E11.329 Type 2 diabetes mellitus with mild nonproliferative diabetic retinopathy without macular edema
- E11.331 Type 2 diabetes mellitus with moderate nonproliferative diabetic retinopathy with macular edema
- E11.339 Type 2 diabetes mellitus with moderate nonproliferative diabetic retinopathy without macular edema
- E11.341 Type 2 diabetes mellitus with severe nonproliferative diabetic retinopathy with macular edema
- E11.349 Type 2 diabetes mellitus with severe nonproliferative diabetic retinopathy without macular edema
- E11.351 Type 2 diabetes mellitus with proliferative diabetic retinopathy with macular edema
- E11.352 Type 2 diabetes mellitus with proliferative diabetic retinopathy with traction retinal detachment involving the macula
- E11.353 Type 2 diabetes mellitus with proliferative diabetic retinopathy with traction retinal detachment not involving the macula
- E11.354 Type 2 diabetes mellitus with proliferative diabetic retinopathy with combined traction retinal detachment and rhegmatogenous retinal detachment
- E11.355 Type 2 diabetes mellitus with stable proliferative diabetic retinopathy

090177e1a5be86fe\Approved\Approved On: 19-Mar-2026 15:57 (GMT)

- E11.359 Type 2 diabetes mellitus with proliferative diabetic retinopathy without macular edema
- E11.36 Type 2 diabetes mellitus with diabetic cataract
- E11.37 Type 2 diabetes mellitus with diabetic macular edema, resolved following treatment
- E11.39 Type 2 diabetes mellitus with other diabetic ophthalmic complication
- E11.40 Type 2 diabetes mellitus with diabetic neuropathy, unspecified
- E11.41 Type 2 diabetes mellitus with diabetic mononeuropathy
- E11.42 Type 2 diabetes mellitus with diabetic polyneuropathy
- E11.43 Type 2 diabetes mellitus with diabetic autonomic (poly)neuropathy
- E11.44 Type 2 diabetes mellitus with diabetic amyotrophy
- E11.49 Type 2 diabetes mellitus with other diabetic neurological complication
- E11.51 Type 2 diabetes mellitus with diabetic peripheral angiopathy without gangrene
- E11.52 Type 2 diabetes mellitus with diabetic peripheral angiopathy with gangrene
- E11.59 Type 2 diabetes mellitus with other circulatory complications
- E11.610 Type 2 diabetes mellitus with diabetic neuropathic arthropathy
- E11.618 Type 2 diabetes mellitus with other diabetic arthropathy
- E11.620 Type 2 diabetes mellitus with diabetic dermatitis
- E11.621 Type 2 diabetes mellitus with foot ulcer
- E11.628 Type 2 diabetes mellitus with other skin complications
- E11.630 Type 2 diabetes mellitus with periodontal disease
- E11.638 Type 2 diabetes mellitus with other oral complications
- E11.641 Type 2 diabetes mellitus with hypoglycemia with coma
- E11.649 Type 2 diabetes mellitus with hypoglycemia without coma

090177e1a5be86fe\Approved\Approved On: 19-Mar-2026 15:57 (GMT)

- E11.65 Type 2 diabetes mellitus with hyperglycemia
- E11.69 Type 2 diabetes mellitus with other specified complication
- E11.8 Type 2 diabetes mellitus with unspecified complications
- E11.9 Type 2 diabetes mellitus without complications

**17.4.2. Medication History**

**17.4.2.1. Systemic Immunomodulators**

The below list includes generic drug names classified by therapeutic use. All associated NDC codes will be utilized. Additional therapies may be added as they are approved.

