### 9.3.3. Covariates

All members of the study cohorts will be described according to covariates identified in the claims data. Demographic attributes will be determined on the vaccination/cohort entry date, while other factors will be assessed in the one year prior to the cohort entry date. Unless specified as for descriptive purposes only, the covariates listed will be included in the PS models. All variables are binary unless otherwise specified.

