#### **Medication History**

- Systemic immunomodulators
- Oral corticosteroids
- Antivirals
- Antibiotics

In addition to the covariates listed above, baseline attributes will be identified on an empiric basis by examining the 25 most frequently occurring diagnoses, drugs dispensed, and procedures (including other baseline vaccinations, as captured through NDC and CPT codes) performed among individuals with and without COMIRNATY 2023-2024 Formula exposure.

These empiric covariates will be considered for inclusion in the PS models if they are potential confounders.

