$$\begin{aligned} & \text{logit}\{P(T_i = 1 \mid \mathbf{X}_i)\} \\ &= \beta_0 + \beta_1 \text{Sex (binary)}_i + \beta_2 \text{Age (categorical)}_i \\ &+ \beta_3 \text{Calendar month (categorical)}_i + \beta_4 \text{Geographic region (categorical)}_i \\ &+ \beta_5 \text{Asthma (binary)}_i + \beta_6 \text{Non-malignant blood disorders (binary)}_i \\ &+ \beta_7 \text{Chronic lung disease (binary)}_i + \beta_8 \text{Down syndrome (binary)}_i \\ &+ \beta_9 \text{Heart disease (binary)}_i \\ &+ \beta_{10} \text{History of SARS-CoV-2 infection (binary)}_i \\ &+ \beta_{11} \text{Immunocompromised status (binary)}_i \\ &+ \beta_{12} \text{Kidney disorders (binary)}_i + \beta_{13} \text{Liver disorders (binary)}_i \\ &+ \beta_{14} \text{Neurological or neurodevelopmental conditions (binary)}_i \\ &+ \beta_{15} \text{Malignant neoplasms (binary)}_i + \beta_{16} \text{Obesity (binary)}_i \\ &+ \beta_{17} \text{Type II diabetes (binary)}_i \\ &+ \beta_{18} \text{Number of hospitalizations in prior year (continuous)}_i \\ &+ \beta_{19} \text{Number of emergency room visits in prior year (continuous)}_i \\ &+ \beta_{20} \text{Number of outpatient encounters in prior year (continuous)}_i \\ &+ \beta_{21} \text{Seasonal influenza vaccination (binary)}_i \\ &+ \beta_{22} \text{RSV vaccination (binary)}_i + \beta_{23} \text{Systemic immunomodulators (binary)}_i \\ &+ \beta_{24} \text{Oral corticosteroids (binary)}_i + \beta_{25} \text{Antivirals (binary)}_i \\ &+ \beta_{26} \text{Antibiotics (binary)}_i + \beta_{27} \text{Identified empiric variables (binary)}_i, \end{aligned}$$

where  $T_i$  denotes exposure status for individual  $i$ , with  $T_i = 1$  indicating a recorded vaccination of the COMIRNATY 2023-2024 Formula and  $T_i = 0$  indicating no recorded vaccination of the COMIRNATY 2023-2024 Formula.

A greedy digit-based matching algorithm will be used, in which patients exposed to the COMIRNATY 2023-2024 Formula are matched without replacement to comparator patients at a given level of precision defined by the number of digits of the PS (Parsons, 2001), to a maximum of 8 decimal places. When no further matches are available at a given level of precision, the number of digits is sequentially reduced until a maximum allowable caliper of 0.1 is reached, thereby ensuring that the matched cohorts are comparable with respect to the underlying measured risk factors. Matching by propensity score will be conducted within

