XW04398	Introduction of Inebilizumab-cdon into Central Vein, Percutaneous Approach, New Technology Group 8

XW043G5	Introduction of Sarilumab into Central Vein, Percutaneous Approach, New Technology Group 5
XW043H5	Introduction of Tocilizumab into Central Vein, Percutaneous Approach, New Technology Group 5
XW043L6	Introduction of CD24Fc Immunomodulator into Central Vein, Percutaneous Approach, New Technology Group 6
XW0DXM6	Introduction of Baricitinib into Mouth and Pharynx, External Approach, New Technology Group 6
XW0G7M6	Introduction of Baricitinib into Upper GI, Via Natural or Artificial Opening, New Technology Group 6
XW0H7M6	Introduction of Baricitinib into Lower GI, Via Natural or Artificial Opening, New Technology Group 6

**CPT**

80145	Adalimumab
80158	Cyclosporine
80169 	Everolimus
80180	Mycophenolate (mycophenolic acid)
80193	Leflunomide
80195	Sirolimus
80197	Tacrolimus
80180	Mycophenolate (mycophenolic acid)
80204	Methotrexate
80230	Infliximab
80280	Vedolizumab

---

 CPT copyright 2024 American Medical Association. All rights reserved.

 CPT copyright 2024 American Medical Association. All rights reserved.

- 90585 Bacillus Calmette-Guerin vaccine (BCG) for tuberculosis, live, for percutaneous use
- 90586 Bacillus Calmette-Guerin vaccine (BCG) for bladder cancer, live, for intravesical use

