**HCPCS**

- J0129 Injection, abatacept, 10 mg (code may be used for Medicare when drug administered under the direct supervision of a physician, not for use when drug is self-administered)
- J0135 Injection, adalimumab, 20 mg
- S0176 Hydroxyurea, oral, 500 mg
- J0215 Injection, alefacept, 0.5 mg
- J0202 Injection, alemtuzumab, 1 mg
- J0480 Injection, basiliximab, 20 mg
- J0485 Injection, belatacept, 1 mg
- J0490 Injection, belimumab, 10 mg
- J0491 Injection, anifrolumab-fnia, 1 mg
- J0638 Injection, canakinumab, 1 mg
- J0717 Injection, certolizumab pegol, 1 mg (code may be used for Medicare when drug administered under the direct supervision of a physician, not for use when drug is self-administered)
- J1300 Injection, eculizumab, 10 mg
- J1302 Injection, sutimlimab-jome, 10 mg
- J1303 Injection, ravulizumab-cwvz, 10 mg
- J1438 Injection, etanercept, 25 mg (code may be used for Medicare when drug administered under the direct supervision of a physician, not for use when drug is self-administered)
- J1442 Injection, filgrastim (G-CSF), excludes biosimilars, 1 mcg
- J1447 Injection, tbo-filgrastim, 1 mcg

J1449	Injection, eflapegrastim-xnst, 0.1 mg
J1595	Injection, glatiramer acetate, 20 mg
J1602	Injection, golimumab, 1 mg, for intravenous use
J1628	Injection, guselkumab, 1 mg
J1745	Injection, infliximab, excludes biosimilar, 10 mg
J1747	Injection, spesolimab-sbzo, 1 mg
J1823	Injection, inebilizumab-cdon, 1 mg
J1826	Injection, interferon beta-1a, 30 mcg
J1830	Injection interferon beta-1b, 0.25 mg (code may be used for Medicare when drug administered under the direct supervision of a physician, not for use when drug is self-administered)
J2323	Injection, natalizumab, 1 mg
J2327	Injection, risankizumab-rzaa, intravenous, 1 mg
J2329	Injection, ublituximab-xiyy, 1mg
J2350	Injection, ocrelizumab, 1 mg
J2355	Injection, oprelvekin, 5 mg
J2504	Injection, pegademase bovine, 25 IU
J2506	Injection, pegfilgrastim, excludes biosimilar, 0.5 mg
J2562	Injection, plerixafor, 1 mg
J2781	Injection, pegcetacoplan, intravitreal, 1 mg
J2793	Injection, rilonacept, 1 mg
J2820	Injection, sargramostim (GM-CSF), 50 mcg
J2860	Injection, siltuximab, 10 mg
J3241	Injection, teprotumumab-trbw, 10 mg

090177e1a5be86fe\Approved\Approved On: 19-Mar-2026 15:57 (GMT)

J3245	Injection, tildrakizumab, 1 mg J3380 Injection, vedolizumab, 1 mg
J3262	Injection, tocilizumab, 1 mg
J3357	Ustekinumab, for subcutaneous injection, 1 mg
J3358	Ustekinumab, for intravenous injection, 1 mg

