J7500-J7599:	Immunosuppressive drugs
J8560	Etoposide, oral, 50 mg
J8610	Methotrexate, oral, 2.5 mg
J9000	Injection, doxorubicin HCl, 10 mg
J9015	Injection, aldesleukin, per single use vial
J9030	BCG live intravesical instillation, 1 mg
J9037	Injection, belantamab mafodotin-blmf, 0.5 mg
J9040	Injection, bleomycin sulfate, 15 units
J9060	Injection, cisplatin, powder or solution, 10 mg
J9065	Injection, cladribine, per 1 mg J9047 Injection, carfilzomib, 1 mg
J9070	Cyclophosphamide, 100 mg
J9071	Injection, cyclophosphamide, (AuroMedics), 5 mg
J9098	Injection, cytarabine liposome, 10 mg
J9100	Injection, cytarabine, 100 mg
J9145	Injection, daratumumab, 10 mg
J9144	Injection, daratumumab, 10 mg and hyaluronidase-fihj
J9153	Injection, liposomal, 1 mg daunorubicin and 2.27 mg cytarabine
J9176	Injection, elotuzumab, 1 mg
J9181	Injection, etoposide, 10 mg

J9190	Injection, fluorouracil, 500 mg
J9205	Injection, irinotecan liposome, 1 mg
J9206	Injection, irinotecan, 20 mg
J9210	Injection, emapalumab-lzsg, 1 mg
J9212	Injection, interferon alfacon-1, recombinant, 1 mcg
J9213	Injection, interferon, alfa-2a, recombinant, 3 million units
J9214	Injection, interferon, alfa-2b, recombinant, 1 million units
J9215	Injection, interferon, alfa-N3, (human leukocyte derived), 250,000 IU
J9216	Injection, interferon, gamma 1-b, 3 million units
J9247	Injection, melphalan flufenamide, 1 mg
J9250	Methotrexate sodium, 5 mg
J9259	Injection, paclitaxel protein-bound particles (American Regent) not therapeutically equivalent to J9264, 1 mg
J9260	Methotrexate sodium, 50 mg
J9264	Injection, paclitaxel protein-bound particles, 1 mg
J9267	Injection, paclitaxel, 1 mg
J9302	Injection, ofatumumab, 10 mg
J9331	Injection, sirolimus protein-bound particles, 1 mg
J9332	Injection, efgartigimod alfa-fcab, 2 mg
J9360	Injection, vinblastine sulfate, 1 mg
J9370	Vincristine sulfate, 1 mg
J9371	Injection, vincristine sulfate liposome, 1 mg
J9380	Injection, teclistamab-cqyv, 0.5 mg

090177e1a5be86fe\Approved\Approved On: 19-Mar-2026 15:57 (GMT)

M0249	Intravenous infusion, tocilizumab, for hospitalized adults and pediatric patients (2 years of age and older) with COVID-19 who are receiving systemic corticosteroids and require supplemental oxygen, non-invasive or invasive mechanical ventilation

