#### **17.4.2.2. Corticosteroids**

AHFS 680400\* Adrenals, restricted to oral routes of administration

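### The propensity-score covariate labelled systemic immunomodulators has no route limit and contains local-use and vaccine codes, so balance in true systemic use is neither assured nor checked

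*Protocol*

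**What the plan says.** Section 9.3.3 (Medication History) lists "Systemic immunomodulators" as a baseline covariate, under the general rule "Unless specified as for descriptive purposes only, the covariates listed will be included in the PS models". Section 9.7.2.1 enters it as one binary term in the single logistic model that produces the master matched cohort. That cohort serves every primary, secondary and subgroup analysis.

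Appendix IV, section 17.4.2.1, builds the covariate from an ingredient list: "The below list includes generic drug names classified by therapeutic use. All associated NDC codes will be utilized". No route or dosage form is specified. Section 17.4.2.1.5 then adds diagnosis, procedure and HCPCS codes. Among them are J2781 ("Injection, pegcetacoplan, intravitreal, 1 mg"), J9030 ("BCG live intravesical instillation, 1 mg"), CPT 90586 (BCG given into the bladder) and CPT 90585 ("Bacillus Calmette-Guerin vaccine (BCG) for tuberculosis, live, for percutaneous use"). BCG vaccine is also on the ingredient list, in 17.4.2.1.1.4.

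The next covariate, in section 17.4.2.2, does carry a route limit on its drug class: "Adrenals, restricted to oral routes of administration".

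**The concern.** A covariate named for systemic use should separate people with systemic immune modulation from people without it. As written, it is also switched on by products placed in the eye or the bladder, and by a vaccine that sections 17.2.2.1 and 17.2.2.2 treat as one of the ordinary vaccines that can qualify a comparator.

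Section 9.7.2.1 judges balance by the standardized difference of each covariate in the model, with 0.1 as the limit. If the flag mixes systemic and local use, and the mix differs between recipients and comparators, the flag can look balanced while systemic use is not. No planned check would show this. Systemic immunosuppression matters for outcomes such as herpes zoster, and it marks the autoimmune and demyelinating diseases on the outcome list.

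**Working it through.** The plan gives no figure to reproduce here. The check has two parts: the text, and a sensitivity calculation on assumed prevalences.

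**Text, side by side**

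- Label: systemic (9.3.3, 9.7.2.1). Definition: all NDCs of each ingredient, no route (17.4.2.1).
- Codes whose own descriptions are not systemic: J2781 (intravitreal), J9030 and 90586 (intravesical).
- Code listed elsewhere as an ordinary vaccine: 90585, in 17.2.2.1. BCG vaccine is likewise in the vaccine list of 17.2.2.2.
- The protocol separates local forms when it wants to: antivirals (17.4.2.3) and antibiotics (17.4.2.4) have their own topical and eye headings.

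**Model**

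Let S be the prevalence of systemic use and L that of local-only use, with r for recipients and c for comparators. Suppose matching balances the pooled flag S + L exactly. Systemic use among matched comparators is then

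S_cm = (S_r + L_r) × S_c / (S_c + L_c).

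The residual standardized difference is (S_r − S_cm) / √{[S_r(1 − S_r) + S_cm(1 − S_cm)] / 2}. For an outcome with risk ratio RR for systemic use, the vaccine rate ratio is multiplied by [1 + S_r(RR − 1)] / [1 + S_cm(RR − 1)].

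**Case A: systemic use 4% in both groups (assumed), immunocompromised term ignored**

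- L 4% vs 2.5%: S_cm = 0.08 × 0.04/0.065 = 4.92%. Standardized difference 0.045 in absolute value. Multiplier 1.04/1.0492 = 0.991 for RR 2, and 1.08/1.0985 = 0.983 for RR 3.
- L 6% vs 3%: S_cm = 0.10 × 0.04/0.07 = 5.71%. Standardized difference 0.080 in absolute value. Multiplier 1.08/1.1143 = 0.969 for RR 3.

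**Case B: systemic use differs before matching (assumed)**

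The last two columns suppose that a fraction k of systemic users is also caught by immunocompromised status and balanced there: S_cm = kS_r + [(1 − k)S_r + L_r] × (1 − k)S_c / [(1 − k)S_c + L_c].

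| S, r vs c | L, r vs c | S_cm (k = 0) | Std. diff., k = 0 | k = 0.5 | k = 0.8 |
|---|---|---|---|---|---|
| 3% vs 2% | 1% vs 1% | 2.67% | 0.020 | 0.015 | 0.009 |
| 3% vs 2% | 3% vs 3% | 2.40% | 0.037 | 0.023 | 0.011 |
| 3% vs 2% | 6% vs 2% | 4.50% | −0.079 | −0.054 | −0.028 |
| 3% vs 2% | 2% vs 6% | 1.25% | 0.122 | 0.064 | 0.027 |
| 5% vs 3% | 2% vs 6% | 2.33% | 0.142 | 0.080 | 0.035 |
| 6% vs 2% | 2% vs 10% | 1.33% | 0.250 | 0.120 | 0.047 |

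With a route limit (L = 0 in both groups), S_cm = S_r and the residual is 0 in this model.

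**Which drugs lean on this flag**

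The HCPCS list for immunocompromised status (17.4.1.7.3) names mainly transplant agents, oral steroids, methotrexate and cyclophosphamide. It does not name the TNF inhibitors (17.4.2.1.2.2), most of the interleukin inhibitors (17.4.2.1.2.3), the interferons (17.4.2.1.1.2), natalizumab or ocrelizumab. For these, k is likely to be low.

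**The case against.** Four counter-arguments carry weight.

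- **Products not named.** A reader might infer that people using eye drops or skin creams for dry eye, eczema or sun damage are shown to be in this covariate, because cyclosporine, tacrolimus and 5-fluorouracil are listed. The documents do not support that. They give bare ingredient names, and whether local NDCs exist for them is outside knowledge. What is documented is intravesical BCG, one intravitreal drug and the BCG vaccine, with no volumes.
- **Matching not shown to fail.** A reader might also infer that matching fails to balance systemic use. Both Case A scenarios stay below the protocol's own 0.1 limit. In Case B, 0.1 is exceeded only where local-only use is three to five times as common in comparators, and with k = 0.5 only the most extreme row still exceeds it.
- **Other terms help.** Immunocompromised status and number of outpatient encounters are both in the propensity score, every comparator must have a healthcare encounter, and frequently dispensed drugs are screened as empiric covariates. The self-controlled analysis does not use this covariate at all.
- **The corticosteroid contrast is partial.** The oral limit there applies to the NDC class only; section 17.4.2.2.1 adds inhaled, intraocular and intravitreal codes to the same covariate. Local procedure codes therefore do not prove what the NDC extract will contain.

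All four stand, and they limit the likely size. They do not remove the contradiction between label and definition, and they do not make an imbalance visible if one occurs.

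**Conclusion.** The point holds as an error of definition. A covariate labelled systemic states no route limit and includes codes that are not systemic on their own descriptions, together with a code that the protocol elsewhere lists as an ordinary vaccine. Balance in true systemic use is not assured, and the planned diagnostics cannot reveal its absence.

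The size cannot be derived from the documents. Under the Case A assumptions the rate ratio shifts by about 1-3%, and overlap with immunocompromised status reduces that. This is far from the safety-signal threshold of a rate ratio above 3.0, and no conclusion is shown to change. It still merits correction because the flag helps form the one master cohort behind all Phase 2 analyses, and because several drug classes depend mainly on it.

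**What to change.** In section 17.4.2.1, restrict the NDC extract to systemic routes of administration. Remove J2781, J9030, CPT 90586 and CPT 90585 from 17.4.2.1.5, and the BCG vaccine entry from 17.4.2.1.1.4. Report the standardized difference for the corrected covariate before and after matching.

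Section 17.4.1.7.4 needs no new rule. Its NDCs are tied to HCPCS entries that mostly state oral or parenteral forms, so it is enough to confirm that the extract follows those forms.

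The cost is a route filter and a few deletions, with no new data. If the propensity score has already been fitted, the model and the matching must be rerun.

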**17.4.2.1.1. Immunomodulators**

**17.4.2.1.1.1. Colony-Stimulating Factors**

ancestim
balugrastim
efbemalenograstim alfa
empegfilgrastim
filgrastim
lenograstim
lipegfilgrastim
molgramostim
pegfilgrastim
pegteograstim
sargramostim

**17.4.2.1.1.2. Interferons**

albinterferon alfa-2b
cepeginterferon alfa-2b
interferon alfa natural
interferon alfa-2a
interferon alfa-2b
interferon alfacon-1
interferon alfa-n1
interferon beta natural
interferon beta-1a
interferon beta-1b
interferon gamma
peginterferon alfa-2a
peginterferon alfa-2a, combinations
peginterferon alfa-2b

090177e1a5be86fe\Approved\Approved On: 19-Mar-2026 15:57 (GMT)

peginterferon alfa-2b, combinations
peginterferon alfacon-2
peginterferon beta-1a
ropeginterferon alfa-2b

**17.4.2.1.1.3. Interleukins**

aldesleukin
oprelvekin

**17.4.2.1.1.4. Other Immunostimulants**

BCG vaccine
cridanimod
dasiprotimut-T
elapegademase
glatiramer acetate
histamine dihydrochloride
immunocyanin
lentinan
melanoma vaccine
mifamurtide
pegademase
pidotimod
plerixafor
polyinosinic:polycytidylic acid (poly I:C)
poly ICLC
roquinimex
sipuleucel-T
tasonermin
thymopentin

**17.4.2.1.2. Immunosuppressants**

**17.4.2.1.2.1. Selective Immunosuppressants**

abatacept
abetimus
alefacept
alemtuzumab
anifrolumab
antilymphocyte immunoglobulin (horse)
antithymocyte immunoglobulin (rabbit)
apremilast
avacopan

090177e1a5be86fe\Approved\Approved On: 19-Mar-2026 15:57 (GMT)

baricitinib
begelomab
belatacept
belimumab
belumosudil
cladribine
deucravacitinib
eculizumab
efalizumab
efgartigimod alfa
emapalumab
everolimus
filgotinib
fingolimod
gusperimus
imlifidase
inebilizumab
itacitinib
leflunomide
muromonab-CD3
mycophenolic acid
natalizumab
ocrelizumab
ofatumumab
ozanimod
peficitinib
pegcetacoplan
ponesimod
ravulizumab
siponimod
sirolimus
sutimlimab
teprotumumab
teriflunomide
tofacitinib
ublituximab
upadacitinib
vedolizumab

090177e1a5be86fe\Approved\Approved On: 19-Mar-2026 15:57 (GMT)

